Other approaches. Rhee et al [20] and Alam et al [25] have also explored EPR in a clinically relevant exsanguination model in pigs. Using readily available equipment, they induced profound hypothermia by aortic flush, both proximally and distally, via a thoracotomy and direct aortic cannulation. They used the Unisol solutions during cooling and rewarming, respectively. Repair of the aortotomy was accomplished during no flow. After total circulatory arrest of up to 30 min, normal neurologic recovery could be achieved [20]. Normal cognitive function after exsanguinating hemorrhage from a vessel injury and prolonged asanguinous low flow (by CPB) at 10°C can also be achieved even after prolonged shock prior to induction of hypothermia. They have explored the rates of cooling and rewarming and found a suggestion that best outcome is with the most rapid cooling [26] and moderately slow rewarming [27].

Comparison to standard therapy. Wu et al [28] compared 1 hour of EPR with standard care (CPR and fluid resuscitation) following cardiac arrest from prolonged hemorrhage (~2 hrs). In the CPR group, spontaneous circulation could not be restored without CPB, but long-term survival could not be achieved despite aggressive intensive care. Even with 1 hour of hypothermic no flow, however, almost all dogs survived in the EPR groups. Early in the study, several EPR animals developed seizures. They postulated that more prolonged post-arrest mild hypothermia might alleviate this deterioration and, therefore, added a third group with 36 hr cooling. This group had significantly better neurologic outcomes than the EPR group with 12 hrs hypothermia.

In summary, outcomes from cardiac arrest in trauma patients with current management strategies are dismal. Laboratory studies from the Safar Center, USUHS, and Massachusetts General Hospital suggest that EPR holds promise for improving these outcomes. Sufficient data are available to develop a clinical feasibility protocol. Additional laboratory studies prior to initiating this study are not justified at this time.

Clinical protocol

Per the request of the FDA, 10 subjects who undergo EPR will be entered and a detailed report will be submitted to the FDA prior to any further subject enrollment. Subjects entered into this trial will have had a left thoracotomy and right tube thoracostomy. Appropriate operative exposure for EPR may require

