The experimental aspects of this protocol that are different from the standard of care for trauma patients include the rapid cooling with the saline flush, reperfusion/rewarming using CPB, post-resuscitation mild hypothermia, and the potential for long-term ECLS. Standard operative management of injuries will occur simultaneously with these components. The experimental treatment will be completed when the subject has been rewarmed to normothermia and is not on ECLS.

Failure of EPR:

Technical issues may lead to inability to initiate adequate cooling for EPR. These issues could include (but are not limited to): inability to place the cannulae (most likely because of the subject's anatomy or specific injury pattern), displacement of cannulae after placement, and inability to establish adequate flow and thus adequate cooling. Minimal cooling rates are defined as achieving Tty 30°C within 15 min, 20°C within 30 min, and 10°C within 60 min. Failure of the pump is also a possibility, although this is unlikely as these devices are used routinely for CPB in the operating room. If EPR cannot technically be adequately induced, the investigator may elect to discontinue resuscitative efforts.

Personnel:

The trauma surgeon and the trauma team will perform the resuscitation. They will place the cannulae and initiate EPR. If possible, a perfusionist may assist with pumping for the cold fluid and with CPB. The cooperation of cardiac surgeons will be needed. A part-time coordinator will be involved in training, stocking the equipment needed for EPR, and collecting data. In addition, the coordinator may participate in EPR induction.

Because this is the first trial of EPR, subjects will not be enrolled when the trained team is not available.

Equipment for EPR:

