Thoracotomy tray and standard trauma resuscitation equipment and supplies will be available per standard care of trauma patients. Specific equipment for this study that will be readily available in the ED will include: large volumes of ice-cold saline in a refrigerator (30 liters stored in a designated refrigerator for this trial), arterial and venous cannulae (various sizes and types), appropriate tubing, CPB pump, and hollow-fiber membrane oxygenator/heat exchangers. This equipment will be stored in a storage area near the trauma resuscitation rooms in the Emergency Department. It will be labeled at the site with the following warning: "CAUTION -Investigational Device/Drug. Limited by Federal (or United States) law to investigational use."

Concurrent Control Group:

We will collect data on concurrent patients who are appropriate candidates for EPR, but do not have EPR initiated because the team is not available. These data will include specifics of resuscitative efforts and the same outcome parameters as the EPR group. Per the request of the FDA, 10 concurrent control subjects will be entered and a detailed report will be submitted to the FDA prior to any further subject enrollment.

Historical Control Group:

Because of concern that bias may influence the selection of subjects who receive EPR, thus affecting the concurrent control group, outcome information regarding similar patients in the trauma registry of the respective institutions (Level I trauma centers) will be obtained. The most recent 100 patients who had undergone an ED thoracotomy will be reviewed. Additional subjects may be required in order to obtain at least 10 subjects who would have met criteria for entry into the study.

Consent:

Due to the emergency nature of the traumatic event and the need for immediate resuscitation, including initiation of EPR, this study must be performed under the Exception from Informed Consent for emergency research as outlined in FDA regulation 21CFR50.24. Once the subject has been stabilized, consent for continued participation in the study for collection of data and long-term follow-up, will be obtained from the subject's legal authorized representative (LAR). In addition, consent for follow up will be obtained for survivors in the control group. (See section X below for additional information regarding the exception from consent conditions, request, and justification.)

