The goal will be to enroll 10 subjects that undergo EPR and 10 concurrent control subjects. A detailed report will be filed with the FDA after the first 5 subjects in each group have been discharged or have expired. A final report will be filed after the hospital courses of 10 subjects in each group have been completed. All interim and outcome reports from the DSMB will also be sent to the USAMRMC ORP HRPO.

Outcome data and data analysis

Survival to hospital discharge without major disability, MODS scores, survival at 28 days, GOSE and SF-36 (at 6 and 12 months) will be compared between groups. Complications felt to be possibly or definitely associated with of the EPR technique will be specifically recorded. As with any cardiac arrest resuscitation trial, there is a risk that a subject will survive with a poor neurologic outcome (e.g., comatose, vegetative). Based on the current literature for survivors of cardiac arrest from trauma with standard card, this risk is small.

The decision to proceed with further clinical investigation of the EPR technique will depend upon the frequency of associated complications (in relation to the high risk of death and morbidity secondary to the original injuries) and lack of inferiority to standard care with regard to the secondary endpoints. Based on information learned during the course of the study, the entry criteria may be revised in order to select subjects most likely to benefit from the intervention. The technique for EPR may also be revised. Evaluating these new criteria or techniques may justify further investigation. If, despite revisions of entry criteria and technique, survival appears to be no better than (or worse than) standard care, the study could be stopped. The FDA, ORP HRPO, and reviewing IRBs will be notified of such revisions prior to their implementation.

VIII. INCLUSION / EXCLUSION CRITERIA

Inclusion criteria

Subjects must meet all of the following inclusion criteria:

- Penetrating trauma with clinical suspicion of exsanguinating hemorrhage
- Age 18-65
- At least 1 sign of life at the scene (pulse, respiratory efforts, spontaneous movements, reactive pupils)
- Loss of pulse <5 min prior to ED arrival or in the ED or operating room
- Thoracotomy performed without immediate return of a palpable pulse in the carotid arteries after clamping the descending thoracic aorta

Exclusion criteria.

Subjects will be excluded for any of the following:

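### The EPR group is counted by treatment received and the controls by candidacy, so an eligible patient in whom EPR is not started although the team is available has no group and no described log

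*Protocol*

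**What the plan says.** **EPR group.** Section VII, Clinical protocol, reports an FDA request: "10 subjects who undergo EPR will be entered and a detailed report will be submitted to the FDA". The enrolment goal under Data and Safety Monitoring Board in the same section uses the same unit: "The goal will be to enroll 10 subjects that undergo EPR and 10 concurrent control subjects". Section IX gives the total as 20.

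**Concurrent controls.** Section VII, in its paragraph on these patients, defines them as follows: "We will collect data on concurrent patients who are appropriate candidates for EPR, but do not have EPR initiated because the team is not available". Absence of the team is the only reason given for not starting.

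**Historical controls.** These are added for a stated reason: "Because of concern that bias may influence the selection of subjects who receive EPR, thus affecting the concurrent control group". They are drawn from recent ED thoracotomy patients and selected by eligibility: "Additional subjects may be required in order to obtain at least 10 subjects who would have met criteria for entry into the study".

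**Failed induction.** Section VII, Failure of EPR, foresees that "Technical issues may lead to inability to initiate adequate cooling for EPR" and lists causes such as failure to place the cannulae or to reach adequate flow. It does not say how such a subject is counted.

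**Who decides, and what is recorded.** Section IX leaves enrolment to the trauma team at the bedside. Section XII provides a case report form for each enrolled subject in both arms. The Appendix A checklist is a bedside eligibility tool and is not described as a log kept for every candidate.

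**What the grouping feeds.** The primary objective in Section VII is to show better survival to discharge without major disability with EPR than in concurrent or historic controls.

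**The concern.** The two sides of the comparison are formed by different rules. A patient enters the EPR side by receiving the treatment and the control side by being a candidate. With the team available, the trauma team can still leave a candidate untreated. Such a patient drops out of the EPR side, whereas the same patient arriving when the team is absent would count as a control. If untreated candidates differ in prognosis from treated ones, the groups differ before EPR has had any effect.

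Two things are at stake. The first is whether the survival comparison can be interpreted: without a record made at the time, nobody can later judge how strong the selection was. The second is the denominator for feasibility, a listed secondary outcome, because the text never says whether a subject with an EPR decision and a failed induction is one of the 10, is additional to them, or is replaced.

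**Working it through.** **The plan's own figure.** 10 + 10 = 20 agrees with Section IX. No power calculation is given, so there is nothing further to reproduce.

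**Step 1. Place each eligible patient under the stated rules.**

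| Team | EPR | Group under the text |
|---|---|---|
| Available | Undergone | EPR |
| Available | Decision made, induction fails | Not stated; EPR group suggested |
| Available | Not started | None |
| Not available | Not started | Concurrent control |

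The third row is empty. For the second row, Section X (item 4) speaks of a decision to enter a patient into the EPR arm, and Appendix B has separate times for the EPR decision, cannula placement, flush start and goal temperature. Both suggest that failures stay in the EPR arm, but neither is a counting rule.

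**Step 2. Size of the selection effect if EPR has no effect.** Let p be survival in all eligible patients seen with the team available, x the share not started, and s survival in that share. Survival among those started is

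(p − x·s) / (1 − x).

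Inputs: p = 9%, the penetrating-trauma rate in the Section VII Rationale. It is a survival rate that includes patients this trial would exclude, so it only stands in for the primary outcome. The documents give no value for x or s; x = 10% and 30% are assumptions.

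- All non-started patients die (s = 0): 0.09/0.9 = 10.0% and 0.09/0.7 = 12.9%. Expected survivors in 10 are 1.00 and 1.29 against 0.90, a shift of 0.10 or 0.39. The binomial SD is √(10 × 0.09 × 0.91) = 0.905.
- Other baselines from the Rationale, s = 0: p = 4% (gunshot) becomes 4.4% or 5.7%; p = 12% (signs of life on arrival) becomes 13.3% or 17.1%. The ratio 1/(1 − x) is 1.11 or 1.43 whatever the baseline.
- Non-started patients fare like the rest (s = p): no bias.
- Non-started patients fare better. For illustration, take s = 17%, the Rationale's stab-wound rate: (0.09 − 0.017)/0.9 = 8.1% and (0.09 − 0.051)/0.7 = 5.6%. The bias is now downward.

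The last case is possible under the inclusion criterion as listed: "Thoracotomy performed without immediate return of a palpable pulse in the carotid arteries after clamping the descending thoracic aorta". It requires only that no pulse returns immediately, so a patient could qualify, regain a pulse before the flush, and never be started.

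**Step 3. Feasibility denominator.** Suppose 1, 2 or 3 failed inductions (assumed) beside 10 successes, with every EPR decision counted. The Clopper-Pearson 95% limits are the Beta(10, n − 9) 2.5% quantile and the Beta(11, n − 10) 97.5% quantile:

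- 10/11 = 91% (59-100%)
- 10/12 = 83% (52-98%)
- 10/13 = 77% (46-95%)

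**Step 4. Is one eligibility rule applied to both groups?** The narrative in Section VIII adds a condition that the injuries cannot readily be repaired through the thoracotomy. The inclusion and exclusion lists and Appendix A omit it. Appendix A also specifies an ED thoracotomy where the list does not restrict the location. The five-minute exclusion runs to the decision to switch to EPR, and the text does not say how that time is set for a control.

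**The case against.** **The empty cell is narrow.** Many patients not started with the team present are simply ineligible: non-survivable injury, asystole, an arch injury that precludes the flush, or too long without signs of life. This stands. What remains is a fully eligible patient with no attempt, at a frequency the documents do not give.

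**The protocol already sees the problem.** It admits selection bias and adds historical controls, and the DSMB discusses each of the first 5-10 enrolled subjects. But historical controls are again selected by candidacy, and the DSMB case discussion covers only enrolled subjects.

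**This belongs in the SAP.** The choice of analysis sets may well sit there. Who is entered, counted and recorded does not, because no analysis can recover patients who were never logged.

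**Stronger readings that the documents do not support.**
- A reader might infer that EPR survival must be inflated. The sign is unknown, as Step 2 shows.
- A reader might infer that failed inductions are discarded, so that feasibility is 10/10 whatever happens. That reading is strained: the failure section treats these patients as subjects, and feasibility of induction would be an empty outcome if they were dropped.
- A reader might point to missing fields on the case report form. The form is broken in extraction, so absent fields are weak evidence.
- A reader might argue that a few uncounted deaths would overturn a significant result. For example, 5/10 against 0/10 gives Fisher p = 0.033, and 5/15 gives p = 0.061. That needs an assumed result and five assumed deaths, and the protocol states no test or alpha.
- A reader might see a contradiction between planning to enrol controls and this sentence under Personnel: "Because this is the first trial of EPR, subjects will not be enrolled when the trained team is not available". In that place it probably means enrolled for EPR. It needs tidying but adds no weight here.

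**Conclusion.** The point holds and should be fixed. The EPR group is defined by receipt and both control groups by candidacy. An eligible patient not started with the team available has no group, and no log is described. The primary comparison is therefore open to a selection bias of unknown size and sign. On the assumed shares of 10% and 30%, with all non-started patients dying, 9% becomes 10.0% or 12.9%. That is at most 0.39 expected survivors in 10 against an SD of 0.905, so probably less than sampling noise. The bias is nil if these patients fare like the rest, and reversed if they fare better.

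The case for change rests on two points instead: selection cannot be judged afterwards without a contemporaneous record, and the feasibility denominator is implied rather than stated. The confidence is medium, because the frequency of such patients is unknown.

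**What to change.** 1. Keep a log at each site of every patient who meets the eligibility criteria, with team availability and, where EPR is not started, the reason.
2. State that every subject with an EPR decision stays in the EPR group and in the feasibility denominator, whether or not induction succeeds. Keep the FDA target of 10 who undergo EPR, and note that the EPR group may then exceed 10. With two failures, for example, 12 + 10 = 22, so the total of 20 in Section IX needs matching wording.
3. Report the survival comparison by team availability (all eligible patients with the team available against all eligible patients without it) beside the result for those who underwent EPR.
4. Apply one version of the criteria and one recorded time point to both groups. The Section VIII narrative, the inclusion and exclusion lists and Appendix A must be reconciled. Which clinical condition should prevail is for the investigators, and none is preferred here. State how the EPR decision time is completed for a control.

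**Cost.** A short log, two recorded items (team availability and reason not started) and revised wording. The downside is some dilution of the contrast by patients in whom EPR is not started, which is why both results should be shown.

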Renal (serum creatinine - µmol/l)	< 1.1	1.2-2.3	2.4-3.9	4.0-5.6	>5.7
Hepatic (serum bilirubin - µmol/l)	< 1.1	1.2-3.5	3.6-7.1	7.2-14.1	>14.2
Cardiovascular (PAR*)	< 10.0	10.1-15.0	15.1-20.0	20.1-30.0	>30.0
Hematologic (platelet count –x 10 ⁻³)	>120	81-120	51-80	21-50	< 20

Primary objective

To demonstrate better survival to hospital discharge without major disability (Glasgow Outcome Scale-Extended >5) after resuscitation with EPR in exsanguinating trauma patients, compared to concurrent or historic control patients.

Secondary objective(s)

To examine the feasibility and safety of rapidly inducing profound cerebral hypothermia for EPR in exsanguinating trauma patients.

To examine 28-day survival, 6 and 12 -month neurologic functional outcome (Glasgow Outcome Score Extended [GOSE]) and SF-36, and the development of multiple organ dysfunction syndrome (MODS) in the EPR group, as compared to a concurrent control group.

Specific complications related to the implementation of EPR and CPB, such as vascular injuries, will be identified.

Data and Safety Monitoring Board.

This study will be monitored by a Data and Safety Monitoring Board (DSMB), which will include researchers with experience in resuscitation research from institutions not involved in the conduct of this clinical trial. At least one member of the DSMB will be a cardiothoracic surgeon.

At a minimum, the DSMB will be convened by teleconference or in person at least yearly. For the first 5-10 subjects enrolled in the trial (both EPR and control groups), the DSMB and the investigators will discuss each case by teleconference contemporaneously (within 30 days of subject enrollment). The DSMB will review each report submitted by the investigators to the FDA.

The DSMB will have the responsibility of making recommendations to the investigators and FDA regarding:

· Enrollment criteria, including inclusion and exclusion of subjects

- Technique used for induction of EPR and CPB for reperfusion
- Post-resuscitation mild hypothermia
- Outcome evaluations
- Patient safety
- Informed consent
- Performance of individual centers

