- No signs of life for greater than 5 min prior to the decision to initiate EPR. This time frame is defined as the time from loss of pulse to the decision to switch to EPR.
- Age is >65 years or <18
- Obvious non-survivable injury
- Suggestion of traumatic brain injury, such as significant facial or cranial distortion
- Electrical asystole
- Rapid external assessment of the injuries suggests massive tissue trauma involving multiple body regions (for example, a crushed limb, distorted chest anatomy, or pelvic instability).

Pregnancy

- Prisoners
- Those with aortic arch injury that would preclude flush should be excluded from study participation.
- Active Military personnel

Based on clinical experience and published data, we believe that the most appropriate candidates for EPR would be subjects who have suffered a cardiac arrest from trauma, presumably from exsanguination, and do not respond to standard resuscitative efforts, including thoracotomy in the ED or operating room. Because of the need to conduct this study under the exception from informed consent, adults (>18 yo) will be included. To include subjects in this feasibility trial with the greatest potential for benefit, we will only include subjects with penetrating trauma. Subjects must be in cardiac arrest in the ED or operating room, as documented by the absence of a pulse in the femoral and carotid arteries. Standard resuscitation would include rapid fluid resuscitation and a thoracotomy with right tube thoracostomy. Subjects would become eligible for EPR if they do not respond immediately to these maneuvers and the injuries cannot readily be repaired via the thoracotomy (e.g., a stab wound to the heart for which the tamponade can readily be released and the wound quickly closed).

A checklist (Appendix A) will be utilized to guickly determine subject eligibility.

Subjects known to be prisoners upon admission will be excluded from the study. But if a subject is taken into custody after being enrolled in the study, we will continue to collect data (includes medical record review and review of their vital status).

IX. SUBJECT RECRUITMENT & SCREENING

Screening procedures

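### Section VIII admits thoracotomy in the ED or operating room, but the Appendix A checklist and the historical-control sampling frame name ED thoracotomy only

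*Protocol*

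**What the plan says.** **Section VIII, inclusion criteria.** The pulse criterion reads "Loss of pulse <5 min prior to ED arrival or in the ED or operating room". The thoracotomy criterion reads "Thoracotomy performed without immediate return of a palpable pulse in the carotid arteries after clamping the descending thoracic aorta" and names no location.

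**Section VIII, narrative after the exclusion list.** Candidates are those who fail standard efforts, "including thoracotomy in the ED or operating room". It adds: "Subjects must be in cardiac arrest in the ED or operating room". It also makes eligibility depend on the injury not being one that can be quickly repaired through the thoracotomy. It names the Appendix A checklist as the tool for deciding eligibility quickly.

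**Section VII, Clinical protocol.** Transport to the operating room is described with an allowance for subjects who are already there.

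**Appendix A.** The pulse line is the same as in section VIII, operating room included. The thoracotomy line repeats the section VIII criterion but puts ED in front of it.

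**Section VII, Historical Control Group.** The reason given for this group is "Because of concern that bias may influence the selection of subjects who receive EPR". The source is "The most recent 100 patients who had undergone an ED thoracotomy will be reviewed". More records may be examined to reach at least 10 "subjects who would have met criteria for entry into the study".

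**Section VII, Concurrent Control Group.** These are appropriate EPR candidates not treated because the team is absent. No ED limit is stated.

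**Section VII, Primary objective.** EPR is to be "compared to concurrent or historic control patients".

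**The concern.** The comparison is not randomised, so its credibility rests on the three groups being drawn from the same population. The historical group was added to guard against selective enrolment. It does that only if the entry criteria applied to old records are those applied to EPR subjects, and if the records searched could contain the same kinds of patient.

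The protocol leaves both conditions open on one visible feature, the place of the thoracotomy. Staff working from section VIII and staff working from the checklist can reach opposite decisions on the same operating-room subject. A person abstracting historical charts has the same problem and, in addition, starts from a list that is ED-only by construction.

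**Working it through.** The protocol states no figure to reproduce here, so the check sets the texts side by side.

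**Step 1. Location allowed by each source**

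| Source | Loss of pulse | Thoracotomy |
|---|---|---|
| Section VIII, criteria list | Shortly before ED arrival, ED or operating room | Not stated |
| Section VIII, narrative | Arrest in ED or operating room | ED or operating room |
| Appendix A checklist | Shortly before ED arrival, ED or operating room | ED |
| Concurrent controls | Follows EPR candidacy | Follows EPR candidacy |
| Historical frame | Not stated; entry criteria applied afterwards | ED |

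**Step 2. Three kinds of subject, other criteria met**

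- Arrest before arrival or in the ED, thoracotomy in the ED: eligible under section VIII, passes the checklist, and is in the historical frame. No conflict.
- Arrest in the operating room, thoracotomy in the operating room: eligible under section VIII, passes the checklist's pulse line, fails its thoracotomy line, and is not in the historical frame as written.
- Arrest in the ED, thoracotomy in the operating room: eligible on the section VIII narrative, fails the checklist's thoracotomy line, and is not in the frame as written.

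The second case also shows that the checklist disagrees with itself: one line admits operating-room arrest and another requires the thoracotomy to be in the ED.

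**Step 3. Effect on the historical group**

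The group is formed as frame first, entry criteria second. Applying criteria can remove records from the frame but cannot add any. Operating-room cases could therefore enter only through the extension that allows additional subjects, and that sentence does not say where those subjects come from.

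- If section VIII governs, the EPR and concurrent groups can include operating-room thoracotomies, while the 100 records first reviewed do not.
- If the checklist governs, the historical frame matches, but some subjects admitted by section VIII fail screening.

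Under neither reading do section VIII, the checklist and the frame all agree.

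**Step 4. How much could be affected**

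Section IX plans 10 EPR subjects. If k of them had an operating-room thoracotomy, the share of a type that the ED frame does not sample is k/10. The protocol gives no k, so the values here are assumptions: k = 0, 1, 2, 3 or 5 gives 0%, 10%, 20%, 30% or 50%. This is a share of subjects with no match on location. It is not a bias estimate.

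**Step 5. A related gap in the criteria**

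The condition about readily repairable injuries stands in the section VIII narrative but in neither the criteria list nor Appendix A. Someone selecting controls from the list or the checklist could leave it out, whereas a surgeon following the narrative would apply it to EPR subjects.

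**The case against.** The strongest reply is that this is a drafting slip. Section VIII requires subjects to meet all its criteria, the checklist is only an aid for applying them, and the checklist itself still admits operating-room arrest. The section VIII bullet is silent on location, so the contradiction lies between the narrative and one added term in the appendix. The case report form supports the idea of a loose label: its only page with cannula and flush times is headed for ED thoracotomy, although the clinical text expects some subjects to be in the operating room already. The historical group is first described as similar patients in the trauma registry, and the extension is not restricted to ED cases. Concurrent controls carry no ED limit. The decision to proceed rests on complications and on lack of inferiority on the secondary endpoints, in a trial of 10 EPR subjects and 10 concurrent controls.

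Much of this stands. The conflict is narrow, and it may well be unintended. But no passage reconciles the texts, and the narrative that names both locations also sends staff to the checklist that names one. If it is a slip, correcting it is all the easier. The primary objective still names historic controls as a comparator.

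Three stronger readings are tempting and not supported:

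- *The historical group can never contain an operating-room case.* The extension sentence is open. Adding older ED cases is its natural reading, but it does not exclude others.
- *Eligible subjects will be turned away.* That is possible if staff follow the checklist literally. The protocol does not show that they will.
- *The mismatch favours EPR.* Section VII cites survival of 12% with signs of life on arrival and 3% without. Those figures come from ED thoracotomies and contrast arrival status, not location. A patient who arrives with signs of life and arrests in the ED is inside the historical frame, so the contrast says nothing about ED versus operating room.

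**Conclusion.** The point holds as an internal inconsistency that affects a named comparator. Section VIII and the checklist give opposite answers for a subject whose arrest and thoracotomy both occur in the operating room. If such subjects are enrolled, the EPR and concurrent groups can include a type of case that the historical frame, as written, does not sample.

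The size and direction of any resulting bias are unknown: the protocol gives no expected number of operating-room cases and no outcome by location. If none occur, the comparison is unaffected and only the wording is at fault. The conclusion assumes that the section VIII narrative is meant to be operative and that the historical frame is applied as stated. It should be corrected before historical records are selected; it does not by itself invalidate the design.

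**What to change.** 1. Reconcile the Historical Control Group text, the section VIII criteria list, the section VIII narrative and Appendix A into one statement of thoracotomy location. The clinical rule is for the investigators to decide.
2. Use that same criteria set in section VIII, in Appendix A and in selecting both control groups. State in it whether the narrative's condition on readily repairable injuries is a criterion.
3. Make the historical sampling frame match the reconciled location, and say which records the extension to at least 10 eligible patients may draw on.
4. Make the ED thoracotomy page heading in Appendix B match.
5. Report thoracotomy location by group, so that any remaining difference in case mix is visible.

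The cost is wording in the criteria, the checklist and one form heading. If operating-room cases are kept, the registry search becomes somewhat wider.
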